### **9.9.3. Analysis for Secondary endpoints**

The occurrence of serious AEFIs will be assessed throughout the entire follow-up period in all enrolled subjects. Serious AEFIs will be further evaluated for their clinical relevance and relationship to vaccination.

The occurrence of pIMD(s) will be collected and summarized through the entire follow-up period in all enrolled subjects.

The PO and congenital anomalies will be summarized when *Cervarix* is administered within 60 days before pregnancy onset or any time during pregnancy. In addition, the PO

will be summarized by the time of the vaccination, such as vaccination before the pregnancy, vaccination during the first trimester of the pregnancy, vaccination during the second trimester of the pregnancy etc.

All secondary endpoints (serious AEFIs, pIMDs and POs) will be summarized by percentage of subjects reporting the endpoint with exact 95% CI.

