- Vaccination schedule: Chinese female subjects aged between 9 and 45 years, who consented to participate in the study, are expected to receive three doses of *Cervarix* at 0, 1 and 6 months. The second dose can be administered between 1 month and 2.5 months after the first dose and the third dose between 5 and 12 months after the first dose. The vaccine will be administered intra-muscularly, in the deltoid region of the upper arm.

Note: Cervarix will be available for purchase at immunisation centres or Point of Vaccination (POV).

- Data collection: electronic Case Report form (eCRF) will be used to collect data.
- Study duration: The follow-up will be performed from enrolment until either 12 months following the third immunisation or 24 months following the first immunisation with *Cervarix* (whichever occurs first). This represents an individual subjects' total follow-up time between 18 and 24 months for subjects completing the immunisation course (3 doses) as per *Cervarix* PI schedule. Subjects who report exposure to *Cervarix* during pregnancy or pregnancy onset up to 60 days following the last immunisation will be followed-up till end of pregnancy, to observe the PO and for any possible congenital anomalies diagnosed during the first 12 months of the child's life. Thus, in such cases, an extended follow-up beyond 24 months may occur.
- Epoch 001: Prospective data collection (for each subject) starting at Visit 1 (Day 1) and ending either 12 months following the third immunisation or 24 months following the first immunisation with *Cervarix*, whichever occurs first.

The study cohorts and epoch foreseen in the study are presented in [Table 1](#).

Table 1 Study groups and epochs foreseen in the study

Study Group	Number of subjects	Age (Min/Max)	Epochs
			Epoch 001
HPV group	3000	09 years - 45 years	x

The following group names will be used in the TFLs, to be in line with the T-domains:

Group order in tables	Group label in tables	Group definition for footnote
1	HPV	Subjects who have received Cervarix

CONFIDENTIAL207350 (EPI-HPV-070 VS CN PMS)
Statistical Analysis Plan

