5. STATISTICAL ANALYSES

That standard data derivation rules and stat methods are described in section 10. All analyses will be performed on the exposed set.

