5.4.2. Analysis for Secondary endpoints

The analysis will be based on the ES.

The occurrence of serious AEFIs will be assessed throughout the entire follow-up period. Serious AEFIs will be further evaluated for their clinical relevance and relationship to vaccination.

The percentage of subjects with serious AEFI occurring within the 30-day (Day 1-30) follow-up period will be tabulated with exact 95% CI after any dose.

The occurrence of pIMD(s) will be collected and summarized through the entire follow-up period in all exposed subjects.

The PO and congenital anomalies will be summarized when *Cervarix* is administered within 60 days before pregnancy onset or any time during pregnancy. In addition, the PO will be summarized by the time of the vaccination, such as vaccination before the pregnancy, vaccination during the first trimester (LMP through week 13) of the pregnancy, vaccination during the second trimester (week 14 through week 27) of the pregnancy, vaccination during the third trimester (week 28 through term) of the pregnancy.

All secondary endpoints (serious AEFIs, pIMDs and POs) will be summarized by percentage of subjects reporting the endpoint with exact 95% CI.

CONFIDENTIAL207350 (EPI-HPV-070 VS CN PMS)
Statistical Analysis Plan**5.4.3. Additional considerations**

The percentage of subjects with at least one medically attended non-serious AEFI occurring within the 30-day (Day 1-30) follow-up period will be tabulated with exact 95% CI after any dose.

The percentage of subjects, who have used any medications, that was required to be reported as per protocol, during the whole study period will be tabulated. Medications will be coded using the GSKDRUG dictionary.

All primary and secondary endpoints (medically attended AEFIs, serious AEFIs, , casually related AEFIs , grade 3 AEFIs, pIMDs and POs) will be summarized by percentage of subjects and percentage of doses reporting the symptoms with exact 95% CI.

Incidence and nature of reported AEFIs following each dose and overall will be presented. The analysis will be done for any AEFI, medically attended AEFI within 30 days follow-up period and serious AEFI.

Adverse events will be coded using medical dictionary for regulatory activities - MedDRA classification of System Organ Class and Preferred term.

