8. CHANGES FROM PLANNED ANALYSES

All analyses related to primary and secondary endpoints except on study attrition will be done on the exposed set instead of all enrolled subjects as planned in the protocol.

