10.1.1. Attributing events to vaccine doses

The dose relative to an event is the most recent study dose given to a subject prior to the start of a given event. For example, if the start date of an adverse event is between Dose 1 and Dose 2, the relative dose will be Dose 1.

If an event starts on the same day as a study dose, the relative dose will be derived from the additional information provided in the CRF using the contents of the flag indicating if the event occurred before or after vaccination. If 'after vaccination' is selected, the relative dose for the event will be the one administered on the start day of the event. If 'before vaccination' is selected, the relative dose for the event will be the dose prior to this one.

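### SAP 5.4.3 extends a percentage of doses to pregnancy outcomes, pIMDs and whole-follow-up serious AEFIs, and no text names exposed pregnancies as the denominator for pregnancy outcomes and congenital anomalies

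*SAP*

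**What the plan says.** Protocol 9.9.3 fixes the measure for the secondary endpoints: "All secondary endpoints (serious AEFIs, pIMDs and POs) will be summarized by percentage of subjects reporting the endpoint with exact 95% CI". SAP 5.4.2 repeats that sentence. SAP 5.4.3 (Additional considerations) then covers all primary and secondary endpoints, names serious AEFIs, pIMDs and POs among them, and says they "will be summarized by percentage of subjects and percentage of doses reporting the symptoms with exact 95% CI". It sets no time window. In the protocol's analysis sections a per-dose summary appears only in 9.9.2, for 30-day medically attended AEFIs.

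On the population, SAP 5 states "All analyses will be performed on the exposed set", SAP 5.4.2 repeats this for the secondary endpoints, and SAP 8 confirms it: "All analyses related to primary and secondary endpoints except on study attrition will be done on the exposed set instead of all enrolled subjects".

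On POs, SAP 5.4.2 restricts the summary to pregnancies where vaccination fell "within 60 days before pregnancy onset or any time during pregnancy. In addition, the PO will be summarized by the time of the vaccination". This says which outcomes are counted and how they are split. It does not say what they are divided by.

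On which dose an event belongs to, SAP 10.1.1 says "The dose relative to an event is the most recent study dose given to a subject prior to the start of a given event". The rule has no upper time limit.

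**The concern.** A percentage is interpretable when its denominator is the set of units that could have had the event. A dose followed for 30 days is such a unit for a 30-day AEFI. For the secondary endpoints there are two problems, of unequal weight.

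**POs and congenital anomalies (the main point).** Only a pregnancy exposed to the vaccine in the stated window can contribute a case. The Exposed Set also holds every vaccinated subject who was never pregnant in that window, including girls from age 9, and the dose count holds all of their doses. If the text is programmed as written, even the subject-level row is diluted, so printing it beside the dose row does not help. Protocol 7.1 records that the approval letter asked specifically for information on the effect on POs, including birth defects.

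**Serious AEFIs and pIMDs (the minor point).** These are collected for up to 24 months. Under SAP 10.1.1 an event many months after a dose still counts against that dose, so the per-dose percentage mixes risk periods of very different length.

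**Working it through.** **Method.** Exact 95% limits by Clopper-Pearson, as in SAP 10.1.5.1, for x cases out of n: lower = Beta(0.025; x, n - x + 1), upper = Beta(0.975; x + 1, n - x).

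**Check against the plan.** Protocol Table 5 gives 15 of 3000 subjects as 0.50% (0.28% to 0.82%). The formula gives 15/3000 = 0.500% (0.280 to 0.823), which agrees.

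**POs.** Inputs: 3000 subjects (protocol 9.5.1) and 3 doses each, so at most 3 x 3000 = 9000 doses. The number of exposed pregnancies is not documented; 10, 20 and 50 are assumed, with 2 outcomes in each case.

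| Denominator | 2 outcomes | Exact 95% CI |
|---|---|---|
| 10 exposed pregnancies (assumed) | 20.0% | 2.5 to 55.6 |
| 20 exposed pregnancies (assumed) | 10.0% | 1.2 to 31.7 |
| 50 exposed pregnancies (assumed) | 4.0% | 0.5 to 13.7 |
| 3000 Exposed Set subjects | 0.07% | 0.01 to 0.24 |
| 9000 doses | 0.02% | 0.00 to 0.08 |

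The dilution is the ratio of denominators and does not depend on the number of outcomes. By subject it is 3000/10 = 300-fold down to 3000/50 = 60-fold. By dose it is 9000/10 = 900-fold down to 9000/50 = 180-fold.

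**Serious AEFIs.** Take the plan's 15 cases, each counted against one dose.

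| Denominator | 15 cases | Exact 95% CI |
|---|---|---|
| 3000 subjects | 0.50% | 0.28 to 0.82 |
| 9000 doses (all courses complete) | 0.17% | 0.09 to 0.27 |
| 7500 doses (mean of 2.5 doses, assumed) | 0.20% | 0.11 to 0.33 |

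The per-dose figure is 3000/9000 = 33% of the subject figure, or 3000/7500 = 40% at 2.5 doses per subject.

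**Risk period behind each dose.** On the 0-1-6 month schedule, with follow-up ending 12 months after dose 3, dose 1 carries 1 - 0 = 1 month, dose 2 carries 6 - 1 = 5 months and dose 3 carries 12 months. The spread varies with the schedule, since SAP 3 allows dose 2 at 1 to 2.5 months "and the third dose between 5 and 12 months after the first dose". With doses at 0, 2.5 and 5 months the periods are 2.5, 2.5 and 12 months.

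**Share outside the 30-day windows.** Three windows cover 90 days of about 18 x 30.44 = 548 days, a fraction of 0.164. At a constant rate, 15 x 0.164 = 2.5 of the 15 cases start inside a window and 12.5 outside. All 15 count against a dose under SAP 10.1.1.

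**The case against.** **The per-dose rows are additions.** They stand under Additional considerations, a heading the SAP sets against protocol-planned analyses in its demography and exposure sections. The planned subject percentage stays in SAP 5.4.2 and again in the 5.4.3 sentence itself. SAP 5.4.2 also tabulates 30-day serious AEFIs with an exact CI, and SAP 6 says that all analyses are descriptive. This stands, and it reduces the serious AEFI and pIMD part to a tidy-up.

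**Analysts may use exposed pregnancies anyway.** The exposure restriction and the split by trimester of vaccination point that way. An analysis set does not by itself fix every table's denominator, the table layouts are in a separate document (SAP 10.2), and pregnancies and infants are listed individually, so counts can be recovered. This also stands: the dilution is conditional. It does not remove the point, because the only population the SAP names is the Exposed Set, and no reading makes all doses a suitable denominator for POs.

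**Stronger readings that a reader might infer, and that the documents do not support:**
- *The narrower per-dose interval is false precision.* Width divided by estimate is 1.086 for 15/3000 and 1.089 for 15/9000, so relative precision is unchanged. The interval shrinks only because the denominator grows.
- *The per-dose row will be set against the 1.9% SAE figure from the earlier Chinese trial.* That figure covers 72 months and the protocol itself rescales it to 0.5%, so the subject row is not directly comparable with 1.9% either.
- *The tables will show a false rise in risk from dose 1 to dose 3.* SAP 5.4.3 does say "Incidence and nature of reported AEFIs following each dose and overall will be presented", but such a pattern needs open-ended windows in a layout that is not available here.
- *SAP 8 hides a change.* SAP 8 records a replacement of planned analyses. Other added summaries, such as the age-group tables, are not listed there either.

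**Conclusion.** The point holds in a limited form, with moderate confidence. For POs and congenital anomalies, SAP 5.4.3 together with the Exposed Set statements gives denominators that are not the at-risk group. Followed literally, this lowers the subject percentage 60- to 300-fold and the dose percentage 180- to 900-fold, under the assumed 50 to 10 exposed pregnancies and complete courses. Whether it happens depends on table layouts that are not available here. For serious AEFIs and pIMDs the per-dose percentage can be computed, but it pools periods of about 1, 5 and 12 months and is about one third of the subject percentage (40% at an assumed 2.5 doses per subject). It should not be read as showing that the planned serious AEFI or pIMD result is wrong: the subject-level result is unaffected and is reported alongside.

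**What to change.** Two changes of wording in SAP 5.4.3, with matching edits to the table shells where needed:

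1. Limit the percentage of doses to Day 1-30 AEFI endpoints. Drop it for pIMDs, POs and serious AEFIs over the whole follow-up, and keep the subject percentages of SAP 5.4.2.
2. Report POs and congenital anomalies with exposed pregnancies, under the plan's own exposure definition, as the stated denominator, overall and by timing of vaccination. Record this as a clarification of the protocol's percentage of subjects, since the unit moves from subject to pregnancy.

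The cost is one stated denominator and some removed table rows. No new data are needed, and the planned subject-level results for serious AEFIs and pIMDs do not change.

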2.2.2. Secondary endpoints

- Occurrence, intensity and causal relationship to vaccination of serious AEFI reported during the period starting at the first immunisation and ending either 12 months following the third immunisation or 24 months following the first immunisation with *Cervarix* (whichever occurs first), in all enrolled subjects.
- Occurrence, intensity and causal relationship of pIMDs detected during the period starting at the first immunisation and ending either 12 months following the third immunisation or 24 months following the first immunisation with *Cervarix* (whichever occurs first), in all enrolled subjects.

CONFIDENTIAL207350 (EPI-HPV-070 VS CN PMS)
Statistical Analysis Plan

- Occurrence of PO when *Cervarix* is administered inadvertently within 60 days before pregnancy onset or any time during pregnancy.
- Occurrence of any congenital anomalies when *Cervarix* is administered inadvertently within 60 days before pregnancy onset or any time during pregnancy.

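### SAP 5.4.3 shows serious AEFIs (and any AEFI) by dose with no stated window, so the dose rows cover about 1, 5 and 12 months and are not comparable

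*SAP*

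**What the plan says.** SAP 5.4.3 (Additional considerations) adds a by-dose display: "Incidence and nature of reported AEFIs following each dose and overall will be presented". It then names the classes: "The analysis will be done for any AEFI, medically attended AEFI within 30 days follow-up period and serious AEFI". The 30-day limit stands beside the medically attended class only.

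The serious AEFI endpoint in SAP 2.2.2 runs from the first immunisation, "ending either 12 months following the third immunisation or 24 months following the first immunisation", whichever comes first. SAP 5.4.2 likewise assesses serious AEFIs over all of follow-up. That section does contain a Day 1-30 serious AEFI table, but it is specified after any dose, not dose by dose.

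The attribution rule is in SAP 10.1.1: "The dose relative to an event is the most recent study dose given to a subject prior to the start of a given event". It has no upper time limit. On timing, SAP 3 gives a nominal schedule of 0, 1 and 6 months and allows a range: "The second dose can be administered between 1 month and 2.5 months after the first dose and the third dose between 5 and 12 months", with both intervals counted from dose 1.

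Neither document gives a by-dose window for serious AEFIs, a person-time denominator, or a caution on reading the rows against each other. The table layouts are in a separate TFL document (SAP 10.2), which is not available here.

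**The concern.** Rows of a by-dose table are read against each other. For medically attended AEFIs that is fair, because every dose has the same 30-day window. For serious AEFIs the window is whatever time passes until the next dose, or until follow-up ends, and that time differs greatly between doses. A steady background rate alone would therefore be expected to put few events in the dose 1 row and most in the dose 3 row.

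The study has no control group in which the same gradient would appear and reveal the cause. A reader could take the rise for an effect that builds with successive doses. The any-AEFI rows have the same weakness, because they include events collected over the whole period.

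**Working it through.** **Inputs.** N = 3000 and an assumed serious AEFI proportion of 0.5% over at least 18 months (protocol 9.5.1). Source rate 1.9% over 72 months (same section). Dose timing from SAP 3, end of follow-up from SAP 2.2.2, attribution rule from SAP 10.1.1.

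**The plan's own figure.** Constant-rate scaling gives 1.9% × 18/72 = 0.475%, which rounds to the stated 0.5%. Clopper-Pearson limits for 15/3000 are 0.28% to 0.82%, as in protocol Table 5. The other three rows of that table also reproduce.

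**Attributable time, nominal schedule.** Dose 1: 1 − 0 = 1 month. Dose 2: 6 − 1 = 5 months. Dose 3: 18 − 6 = 12 months.

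**Expected subjects by dose with no vaccine effect.** Constant rate = 0.5%/18 per month; expected = 3000 × rate × months.

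| Dose | Months | Expected of 3000 | Percentage |
|---|---|---|---|
| 1 | 1 | 15 × 1/18 = 0.83 | 0.028% |
| 2 | 5 | 15 × 5/18 = 4.17 | 0.139% |
| 3 | 12 | 15 × 12/18 = 10.0 | 0.333% |

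The dose 3 to dose 1 ratio is 12 and the dose 3 to dose 2 ratio is 2.4. Using 1.9% per 72 months directly gives 0.79, 3.96 and 9.48, with the same ratios.

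**Permitted schedule, three-dose completers.** Dose 1 collects 1 to 2.5 months. Dose 2 collects 2.5 months (5 − 2.5) to 11 months (12 − 1). Dose 3 always collects 12 months.
- Dose 3 to dose 1: 12/2.5 = 4.8 up to 12/1 = 12.
- Dose 3 to dose 2: 12/11 = 1.1 up to 12/2.5 = 4.8.

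**Non-completers.** Protocol Table 2 places the last call at month 24 when the third dose was not given by month 12. The documents give no stopping rate, so these rates are assumptions. A subject stopping after dose 1 contributes 24 months to dose 1. One stopping after dose 2 (given at month 1) contributes 23 months to dose 2. The table shows mean months per recipient of each dose.

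| Stop after dose 1 / dose 2 | Dose 1 | Dose 2 | Dose 3 | Percentages | Dose 3 : dose 1 |
|---|---|---|---|---|---|
| 5% / 5% | 0.95 × 1 + 0.05 × 24 = 2.15 | (0.90 × 5 + 0.05 × 23)/0.95 = 5.95 | 12 | 0.060%, 0.165%, 0.333% | 5.6 |
| 10% / 10% | 0.90 × 1 + 0.10 × 24 = 3.3 | (0.80 × 5 + 0.10 × 23)/0.90 = 7.0 | 12 | 0.092%, 0.194%, 0.333% | 3.6 |

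With 10%/10% and dose 2 at 2.5 months, dose 1 collects 0.90 × 2.5 + 0.10 × 24 = 4.65 months, so the ratio is 12/4.65 = 2.6.

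**Chance variation.** Suppose 15 events fall at random in the proportions 1:5:12. Dose 3 then exceeds dose 1 with probability above 0.99, and the strict order dose 1 < dose 2 < dose 3 appears with probability 0.85. With doses at 2.5 and 12 months (2.5:9.5:12), dose 3 still exceeds dose 1 with probability 0.98. Precision is low: 4/3000 has an exact 95% interval of 0.04% to 0.34%, and 10/3000 has 0.16% to 0.61%.

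**With a common 30-day window.** The same rate gives about 0.82 expected subjects (0.027%) per dose among 3000 recipients, and the ratio is 1.

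**The case against.** **The 30-day limit may be meant for serious AEFIs too.** SAP 5.4.2 already has one serious AEFI table limited to Day 1-30, and the table shells could settle the matter. The wording of 5.4.3 does not say so, however, and the whole-period endpoint favours the unwindowed reading. If 30 days is the intent, the fix only states it.

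**Other outputs give the comparable view.** This stands in part. SAP 5.4.1 tabulates medically attended AEFIs by dose within Day 1-30, and SAP 10.1.2.4 includes serious events in unsolicited summaries unless stated otherwise. Some doubt remains, because protocol 9.3.1.2 has such events reported as serious AEFIs. There is also the Day 1-30 any-dose serious table and a listing of serious AEFIs. A reader might infer that a true excess soon after dose 1 would be hidden. The documents do not support that: it could be obscured in this one table but should still be visible elsewhere.

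**The table is descriptive and the events are few.** True: SAP 6 calls all analyses descriptive, and no comparison between doses is planned. With about 15 events the intervals overlap. That limits the consequence, but it does not make rows of 1, 5 and 12 months comparable.

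**A Day 1-30 split is nearly empty.** Also true, at about 0.8 expected events per dose. Person-time rates would be a legitimate alternative.

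**Conclusion.** The point holds for the by-dose rows for serious AEFI and any AEFI in SAP 5.4.3. Followed as written, the plan sets windows of about 1, 5 and 12 months side by side, and an artefactual rise is expected: about 0.03%, 0.14% and 0.33% with no vaccine effect. This rests on a constant background rate, the planned 0.5%, and completion of three doses at 0, 1 and 6 months.

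A reader might infer that a 12-fold gradient is certain, or that 4.8 is its floor. Neither follows. The range 4.8 to 12 applies to on-schedule completers only, and follow-up of non-completers to month 24 lowers it, to about 2.6 to 3.6 under the assumed 10%/10% stopping. The step from dose 2 to dose 3 can nearly vanish when dose 3 is late (12 against 11 months).

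Nor does the point reach the main results. The primary endpoint (limited to Day 1-30), the whole-period percentage by subject, the listings and the sample size are unaffected. The correction is worth making because the stated rule produces a misleading supplementary table and the change costs little.

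**What to change.** In SAP 5.4.3, restrict the by-dose rows for serious AEFIs and for any AEFI to events with onset on Day 1-30 after that dose. Keep the whole-period serious AEFI percentage by subject, already planned in SAP 5.4.2, without a split by dose. If a whole-period split by dose is wanted, give it per person-time since that dose and footnote the interval lengths.

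The cost is one SAP sentence and one table shell, with no new data. The downside is sparse by-dose serious rows (about 0.8 expected events each); later serious events would appear only in the overall result and the listing.
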